Amendment 5 to the protocol includes updated safety information and revises the existing eligibility criteria regarding patients at risk for pancreatitis. Acute pancreatitis has been reported with brentuximab vedotin in clinical trials and postmarketing experience. Language has been added to the benefit and risk section of this amendment summarizing the potential risk of pancreatitis in this population of patients with cutaneous T-cell lymphoma (CTCL), a non-life threatening disease. In addition, eligibility criteria have been updated to include the exclusion of patients with an elevated lipase value $\geq 3 \times$ the upper limit of normal (ULN) with an amylase level $> ULN$. Lipase and amylase have also been added to the chemistry lab panel.

As part of the screening requirements for this study, fludeoxyglucose positron emission tomography (FDG-PET) scans and computed tomography (CT) scans of the neck, chest, abdomen, and pelvis are performed at screening. Amendment 5 allows for FDG-PET scans that were taken within 8 weeks before signing the informed consent form (ICF) to be used as the screening FDG-PET, and CT scans taken within 4 weeks before signing the ICF to be used as the screening CT scan provided pre-specified conditions are met. This change is made in the interest of patient safety (to avoid unnecessary duplicate scans).

Purposes for Amendment 5

The purposes of this amendment are to:

- Add safety language regarding the potential risk of pancreatitis
- Add lipase values and amylase levels to pancreatitis exclusion criterion
- Add lipase and amylase to the chemistry lab panel
- Revise text regarding timing of FDG-PET and CT scans
- Clarify text regarding follow-up for objective response
- Clarify text regarding timing of clinical laboratory assessments
- Revise timing for exclusion of oral retinoid therapy
- Add a statement regarding the scheduling of pregnancy tests
- Revise the definition of relapse in the text to align with the definition in the response tables
- Add relapse to the list of global response score (GRS) responses
- Clarify text regarding the collection of pharmacokinetic parameters
- Clarify text regarding the amount of blood to be collected for germline DNA assessments
- Clarify text regarding the discontinuation of study drug
- Revise text describing safety analysis
- Revise text describing monitoring of adverse events
- Revise text regarding the recording and reporting of adverse events and serious adverse events (SAEs)

Brentuximab vedotin (SGN-35)

Clinical Study Protocol C25001 Amendment 5, EudraCT: 2010-024215-14

- Replace references to PPD with Millennium Pharmacovigilance or designee
- Update contact information for reporting SAEs
- Correct errors in Background and Study Rationale text and in-text references
- Correct typographical errors, punctuation, grammar, and formatting

For specific examples of changes in text and where the changes are located, see Section [15.6](#).

PROTOCOL SUMMARY

Study Title: A Randomized, Open-Label, Phase 3 Trial of brentuximab vedotin (SGN-35) Versus Physician's Choice (Methotrexate or Bexarotene) in Patients With CD30-Positive Cutaneous T-Cell Lymphoma

Indication: Patients with CD30-positive (CD30+) cutaneous T-cell lymphoma (CTCL) including those with primary cutaneous anaplastic large cell lymphoma (pcALCL) or mycosis fungoides (MF)

Study Objectives

Primary

- To determine objective response rate (ORR), lasting at least 4 months, with brentuximab vedotin in patients with CD30+ MF or pcALCL compared to that achieved with therapy in the control arm

Key Secondary

- To determine complete response (CR) rate with brentuximab vedotin compared to that achieved with therapy in the control arm
- To determine progression-free survival (PFS) with brentuximab vedotin compared to that achieved with therapy in the control arm
- To determine burden of symptoms during treatment with brentuximab vedotin compared to that achieved with therapy in the control arm

Other Secondary

- To assess duration of response with brentuximab vedotin
- To assess duration of skin response with brentuximab vedotin
- To determine event-free survival (EFS) with brentuximab vedotin compared to that achieved with therapy in the control arm
- To describe the pharmacokinetics (PK) of brentuximab vedotin and monomethylauristatin E (MMAE) in blood
- To determine the immunogenicity of brentuximab vedotin
- To assess patient-reported quality of life outcomes
- To assess the safety of brentuximab vedotin

Overview of Study Design: This is an open-label, randomized, multicenter study. All patients must have histologically-confirmed CD30+ MF or pcALCL by central pathology review. CD30 positivity is defined as $\geq 10\%$ target lymphoid cells demonstrating membrane, cytoplasmic, and/or Golgi staining pattern for CD30 at any intensity above background staining as noted on the corresponding negative control. (A minimum of 10% staining in at least 1 sample is required.) Patients are to be stratified by diagnosis: primary cutaneous anaplastic large cell lymphoma (pcALCL) or mycosis fungoides (MF), and randomized to treatment with brentuximab vedotin monotherapy (Arm 1) up to 16 cycles total (48 weeks), or methotrexate (MTX) or bexarotene per physician's choice (Arm 2) up to a total of 48 weeks.

Patients with documented partial response (PR) or CR at the completion of, and after Cycle 3, may continue to receive study drug for up to 16 cycles of treatment with brentuximab vedotin, or 48 weeks of treatment with bexarotene or methotrexate; patients with stable disease (SD) may continue therapy at the discretion of the investigator. Patients with progressive disease (PD) at any time during the study will be discontinued from study treatment (see Section 7.7). Patients with increasing mSWAT prior to assessment at the end of Cycle 3 will be allowed to continue therapy until the Cycle 3 assessment if, in the investigator's opinion, the findings are due to tumor flare rather

Brentuximab vedotin (SGN-35)

Clinical Study Protocol C25001 Amendment 5, EudraCT: 2010-024215-14

than disease progression.

Objective response over the course of the study, per independent review facility (IRF), will be assessed by global response score (GRS), which consists of skin evaluation (modified severity weighted assessment tool [mSWAT]), nodal and visceral radiographic assessment, and detection of circulating Sézary cells (MF only). Objective response will be evaluated at the end of Cycles 3, 6, 9, 12, and 15, and at EOT. All treated patients without disease progression at EOT/ET will then be followed for objective response every 12 weeks for a minimum of 24 months, then every 6 months; or until disease progression or study closure.

All randomized patients will also be followed for survival every 12 weeks for a minimum of 24 months after the EOT visit, and then every 6 months until patient withdrawal, death, or study closure.

Safety will be evaluated by the incidence of treatment-emergent adverse events (TEAEs), severity and type of AEs, and by changes from baseline in the patient's vital signs, ECOG performance status, and clinical laboratory results using the safety population.

Statistical Analysis and Sample Size Determination: The primary endpoint, the proportion of patients achieving an objective response that lasts at least 4 months, per IRF, will be analyzed using a Cochran-Mantel-Haenszel test stratified by baseline disease diagnosis (pcALCL or MF) based on ITT population. The 95% confidence interval of the difference in ORR that lasts at least 4 months per IRF between the 2 treatments will be provided.

[figure not shown]
CR rate, progression-free survival, and changes in symptom domain per Skindex-29 assessment tool are designated as key secondary endpoints. A fixed sequential testing procedure will be used to test between the primary endpoint and the key secondary endpoints; that is, the key secondary endpoints will be tested only if the primary endpoint is statistically significant. To test the key secondary endpoints, a weighted Holm's procedure will be used.

Approximately 124 patients (approximately 62 patients per treatment arm) will be randomized to the study, including a minimum of 30 patients (15 per treatment arm) with pcALCL. The sample size was calculated based on providing 90% power to detect a 30% improvement in ORR, lasting at least 4 months, in the brentuximab vedotin treatment group, assuming ORRs lasting at least 4 months for brentuximab vedotin treatment group and for the MTX or bexarotene alone treatment group are 70% and 40%, respectively. This calculation is based on a two-sided χ^2 test with significance level of $\alpha = 0.05$, and a 10% dropout rate using nQuery Advisor 7.0.

Study Population: Male or female patients at least 18 years of age with a diagnosis of a CD30+ pcALCL who received at least 1 prior systemic therapy or prior radiation therapy, or CD30+ MF who received at least 1 prior systemic therapy for their disease.

Duration of Study: Patients will be screened up to 28 days, receive study drug up to 48 weeks, and have follow-up assessments performed every 12 weeks for a minimum of 24 months after EOT, and then every 6 months until patient withdrawal, death, or study closure, for a total time on study of up to 5 years.

Study Overview Diagram

Schedule of Events

		Screening ^a	Enrollment	Cycle 1 (21-Day Cycle)			Cycle 2 (21-Day Cycle)	Cycle 3-16 (21-Day Cycle)		EOT/ET	PTFU ^b	
	Cycle (C) Day (D) Visit Window	-28 to D1	Within 72 hours of first dose	C1 D1	C1 D2 & 4	C1 D3 & 5	C2 D1	Cx D1	Cx D16- 21	30 days (±2 days) after last dose	Minimum of 24 months	
Baseline	Informed consent	X	Randomization to Study Treatment Arm Arm 1 - brentuximab vedotin or Arm 2 - Methotrexate or Bexarotene									
	Inclusion/exclusion	X										
	Demographics	X										
	Medical history	X										
	Complete physical exam	X										
	Height	X										
	Weight ^c	X		X				X	X		X	
	Pregnancy test ^d	X		X				X	X			
Archived tissue ^e	X											
Safety Assessments	Vital signs ^f	X		X ^f				X	X		X	
	Physical exam including focused lymphoma assessment			X ^g				X	X		X	X
	ECOG performance status	X		X				X	X		X	
	Hematology/serum chemistry ^h	X						X	X		X	
	Urinalysis	X										
	12-lead ECG	X		X ⁱ								
	Immune reconstitution assessment ^l		X				X	X		X		
Disease Assessment	mSWAT and photography ^k	X	X				X	X	X	X	X	
	Circulating Sézary cells	X	X ^l					X ^l		X	X	
	FDG-PET ^m	X										
	CT ⁿ	X							X ⁿ	X ⁿ	X ⁿ	
	Quality of life assessments ^o		X				X	X		X	X	

Brentuximab vedotin (SGN-35)
Clinical Study Protocol C25001 Amendment 5, EudraCT: 2010-024215-14

	Cycle (C) Day (D) Visit Window	Screening ^a -28 to D1	Enrollment Within 72 hours of first dose	Cycle 1 (21-Day Cycle)			Cycle 2 (21-Day Cycle)	Cycle 3-16 (21-Day Cycle)		EOT/ET 30 days (±2 days) after last dose	PTFU ^b Minimum of 24 months	
				C1 D1	C1 D2 & 4	C1 D3 & 5	C2 D1	Cx D1	Cx D16- 21			
	Healthcare Utilization	X		X			X	X		X	X	
	Skin biopsy ^p (CD30 Expression)	X							X ^p	X ^p	X ^p	
	Biopsies for disease assessment ^q			X								
	Disease status/survival ^r								X	X	X	
Treatment	Brentuximab vedotin administration			X			X	X				
	Methotrexate administration ^s			X			X	X				
	Bexarotene administration ^t			Bexarotene is dosed once a day for the course of the study								
	Monitoring of concomitant medications and procedures		Recorded from screening through 30 days after the last dose of study drug.									
	Adverse event reporting ^u		Recorded from first dose of study drug through 30 days after the last dose of study drug.									
	Serious adverse events		Serious adverse events ^v will be collected from signing of the informed consent form through 30 days after the last dose of study drug									
PK/PD	PK sample ^w			X ^w	X ^w	X ^w		X ^w		X		
	CCI											
	Immunogenicity ^y			X				X		X		
	CCI											

Abbreviations: CT = computed tomography; CTACK = cutaneous T cell-attracting chemokine; ECG = electrocardiogram; ECOG = Eastern Cooperative Oncology Group; ET = early termination; EOT = end of treatment; FDG = fluorodeoxyglucose; MRI = magnetic resonance imaging; mSWAT = modified severity weighted assessment tool; PD = pharmacodynamics; PET = positron emission tomography; PK = pharmacokinetics; PTFU = posttreatment follow-up; TARC = thymus and activation regulated chemokine.

Tests and procedures should be performed on schedule, but occasional changes are allowable (± 2 days) for holidays, vacations, and other administrative reasons. If extenuating circumstances prevent a patient from beginning treatment or completing a scheduled procedure or assessment within this time, the patient may continue the study only with the written permission of the project clinician.

a Screening must occur within 28 days prior to randomization.

b All treated patients without disease progression at EOT/ET will be followed for objective response every 12 weeks (± 2 weeks) for a minimum of 24

Brentuximab vedotin (SGN-35)
Clinical Study Protocol C25001 Amendment 5, EudraCT: 2010-024215-14

		Screening ^a	Enrollment	Cycle 1 (21-Day Cycle)			Cycle 2 (21-Day Cycle)	Cycle 3-16 (21-Day Cycle)		EOT/ET	PTFU ^b
	Cycle (C) Day (D) Visit Window	-28 to D1	Within 72 hours of first dose	C1 D1	C1 D2 & 4	C1 D3 & 5	C2 D1	Cx D1	Cx D16- 21	30 days (±2 days) after last dose	Minimum of 24 months

months after the EOT visit, and then every 6 months (± 1 month); or until progressive disease or study closure. All randomized patients will also be followed for survival every 12 weeks (± 2 weeks) for a minimum of 24 months after the EOT visit, then every 6 months (± 1 month) until patient withdrawal, death, or study closure.

- c Weight will be measured at screening, on Day 1 of each treatment cycle, and at EOT. The brentuximab vedotin dose will be adjusted for patients who experience a ≥ 10% change in weight from baseline
- d A serum beta-human chorionic gonadotropin (B-hCG) pregnancy test will be performed during screening only for patients of childbearing potential. A urine pregnancy test will be performed before dosing on Day 1 of all cycles. The results of any pregnancy test must be negative before dosing on Day 1 of all cycles. Additional pregnancy testing may be performed during the study at the discretion of the investigator, upon request of the Independent Ethics Committee (IEC)/Institutional Review Board (IRB), or if required by local regulations.
- e If available and consistent with local regulations, tumor tissue collected at the time of original diagnosis (unstained slides or a paraffin-embedded block) will be obtained during screening after the patient has signed the informed consent form. The sample may be used in the evaluation of a diagnostic test to determine CD30 expression.

CCI

- f Perform vital signs measurement at screening, prior to dosing on Day 1 of each cycle, and at EOT. On Cycle 1, Day 1 only, also perform vital signs measurements at 1 hour (± 10 minutes) postdose for patients receiving brentuximab vedotin. Blood pressure should be determined with the patient in a seated position after the patient has been sitting quietly for 5 minutes.
- g The Cycle 1, Day 1 physical examination is not required if the complete physical examination performed at screening was conducted within 4 days before randomization. A limited physical exam may be administered at the treating physician's discretion.
- h A blood sample for hematology and serum chemistry will be obtained at screening, before dosing on Day 1 of all cycles, and at EOT. For screening, labs must be performed within 4 days of randomization, and do not need to be repeated before dosing.
 Hematology panel includes complete blood count (CBC) with differential consisting of the following: hemoglobin, hematocrit, platelet count, leukocytes with differential, and neutrophils (absolute neutrophil count [ANC]). Machine counts are acceptable.
 Serum chemistry panel includes: sodium, potassium, carbon dioxide, chloride, blood urea nitrogen (BUN), creatinine, total bilirubin, alkaline phosphatase (ALP), aspartate transaminase (AST), alanine transaminase (ALT), lactate dehydrogenase (LDH), albumin, glucose, urate (uric acid), calcium, phosphate, magnesium, GGT, amylase, and lipase.
 Hemoglobin A1C will be obtained at screening and on Day 1 of Cycles 1, 4, 7, 10, and 16.
 Lipid panel (total cholesterol, HDL, LDL, triglycerides) and thyroid panel (TSH, free T4, free T3) should be obtained at screening and on Day 1 of Cycles 1, 2, 3, 6, 9, 12, and 16.
- i A 12-lead ECG will be obtained at screening and on Cycle 1, Day 1 (predose). ECG assessments are to be performed with the patient supine and rested for 5 minutes and before any closely timed PK blood collection.

Brentuximab vedotin (SGN-35)

Clinical Study Protocol C25001 Amendment 5, EudraCT: 2010-024215-14

		Screening ^a	Enrollment	Cycle 1 (21-Day Cycle)			Cycle 2 (21-Day Cycle)	Cycle 3-16 (21-Day Cycle)		EOT/ET	PTFU ^b
	Cycle (C) Day (D) Visit Window	-28 to D1	Within 72 hours of first dose	C1 D1	C1 D2 & 4	C1 D3 & 5	C2 D1	Cx D1	Cx D16- 21	30 days (±2 days) after last dose	Minimum of 24 months

- j Lymphocytes counts, phenotypic T, B, and natural killer (NK) cell subsets (CD4⁺ T cells counts, CD8⁺ T cells counts, CD8/CD4 ratio, CD19⁺ B cells counts); NK cells (CD3⁻ CD56 CD16⁺ vs CD3⁻ CD56 CD16⁻).
- k The mSWAT should follow guidelines from Olsen, et al, 2011, for analysis and response. Each of the designated index lesions (up to a total of 5) and lesions selected for biopsy will be serially photographed at screening; before dosing on Day 1 of Cycles 1, 2, and 3; at the end of every cycle beginning at Cycle 3 (Days 16-21 or before dosing on Day 1 of the subsequent cycle); within 30 days after the last dose of study drug; and at posttreatment follow-up visits. Full body global photographs including head, trunk, legs, front, back, and side, will be taken at the same time points indicated above.
- l A blood sample for Sézary cell enumeration in patients with MF will be collected at screening; at the time of response assessments at the end of Cycles 3, 6, 9, 12, and 15 (Days 16-21 or before dosing on Day 1 of the subsequent cycle); at EOT; and every 12 weeks (± 2 weeks) for a minimum of 24 months after the EOT visit, and then every 6 months (± 1 month); or until progressive disease or study closure. If the screening sample was obtained within 4 days before randomization, it does not need to be repeated on Cycle 1, Day 1. The Sézary cell sample will be evaluated per independent pathology review and will not be used for dosing decisions; the slide should be prepared from the same vial of blood sent for CBC testing. Investigators should ensure the result of a Sézary cell sample sent for local testing is available prior to dosing.
- m FDG-PET scans will be taken at screening. No further FDG-PET scans will be required unless they are clinically indicated. FDG-PET scans taken within 8 weeks before signing the informed consent form (ICF) may be used as the screening FDG-PET scan.
- n CT scans of the neck, chest, abdomen, and pelvis will be obtained at screening. CT scans taken within 4 weeks before signing the ICF may be used for the screening CT scan if all of the following conditions are met:
- There is no nodal or visceral involvement noted
 - There is no clinically evident lymphadenopathy or splenomegaly by physical exam at the time of screening
 - The scan meets all quality criteria as outlined in the Imaging Manual
- For patients without nodal or visceral involvement (as determined by baseline CT scans), CT scans will be performed:
- During the cycle following the first skin response, ideally corresponding to the confirmation of the skin response, and 6 cycles (a minimum of 4 months) after that confirmed skin response
 - If there is a question of new or progressive disease in the LN/viscera
- For patients with baseline nodal/visceral disease, CT scans will be performed:
- At the end of Cycles 3, 6, 9, 12, and 15 (Days 16-21 or on Day 1 of the subsequent cycle), and per the follow-up schedule until disease progression
 - If there is a question of new or progressive disease in the LN/viscera
 - At EOT if the previous CT scan was performed more than 8 weeks before EOT
- o All questionnaires should be completed on Day 1 of Cycles 1, 2, 4, 6, 8, 10, 12, 14, and 16 before any other study procedures are performed, at EOT, and during posttreatment follow-up. EQ-5D, FACT-G, and Skindex-29 questionnaires will be employed for health-related quality of life (HRQoL) assessment from the patient’s perspective. Questionnaires may be collected by phone or by mail for patients not required to return to clinic for posttreatment follow-

Brentuximab vedotin (SGN-35)
Clinical Study Protocol C25001 Amendment 5, EudraCT: 2010-024215-14

		Screening ^a	Enrollment	Cycle 1 (21-Day Cycle)			Cycle 2 (21-Day Cycle)	Cycle 3-16 (21-Day Cycle)		EOT/ET	PTFU ^b
	Cycle (C) Day (D) Visit Window	-28 to D1	Within 72 hours of first dose	C1 D1	C1 D2 & 4	C1 D3 & 5	C2 D1	Cx D1	Cx D16- 21	30 days (±2 days) after last dose	Minimum of 24 months

up.

- p Skin biopsies with a minimum of 2-mm diameter (at least 2 samples from separate lesions for patients with MF, and at least 1 sample for patients with pcALCL) will be obtained at screening (within 28 days prior to randomization) to confirm tumor specific CD30+ expression and again at the end of Cycle 3, and at the time of disease progression (EOT or during the posttreatment follow-up period). If possible, repeat skin biopsies should be taken from the same lesions as the samples obtained at screening. At the time of PD, an effort should be made to take an additional sample from a new lesion. In the event that a patient is rescreened, repeat skin biopsies should be discussed with the sponsor, project clinician, or designee.
- q If applicable, biopsies for response assessment may be needed as outlined in Section 7 (refer to the following tables):
- Bone marrow: Refer to [Table 7-5](#)
 - Lymph node: Refer to [Table 7-3](#)
 - Skin: Refer to [Table 7-2](#)
 - Viscera: Refer to [Table 7-4](#)
- r Response to treatment (CR, PR, SD, PD, relapse) will be monitored on a continual basis. For all treated patients, GRS will be assessed at the end of Cycles 3, 6, 9, 12, and 15 (Days 16-21 or before dosing on Day 1 of the subsequent cycle), at EOT; and then every 12 weeks for a minimum of 24 months, and then every 6 months; or until disease progression or study closure. All randomized patients will also be followed for survival every 12 weeks for a minimum of 24 months after the EOT visit, then every 6 months until patient withdrawal, death, or study closure. Additional unscheduled GRS determinations may occur following a change in response in skin or at the time of a CT scan. Information may be collected by phone for patients with progressive disease.
- s Methotrexate will be administered once weekly as an oral dose.
- t Patients taking bexarotene will receive fenofibrate for a total of 7 days before the start of bexarotene dosing.
- u All events relating to peripheral neuropathy regardless of seriousness will be followed for all changes in severity until resolution to baseline or study closure, whichever occurs first.
- v Including serious pretreatment events; see Section 10.1.1 and Section 10.3 of the study protocol.
- w Patients randomized to brentuximab vedotin will be assigned to Group A or Group B at the time of randomization for PK sampling. PK blood samples will be obtained at the following times:
- All brentuximab vedotin-treated patients:**
Cycles 1, 3, 5, 7, 9, 11, 13, and 15
Day 1: within 4 hours before the start of the brentuximab vedotin infusion and 30 minutes (± 25 minutes) after the end of the brentuximab vedotin infusion
End of Treatment Visit
- Group A (consisting of half the brentuximab vedotin-treated patients):**

Brentuximab vedotin (SGN-35)
Clinical Study Protocol C25001 Amendment 5, EudraCT: 2010-024215-14

		Screening ^a	Enrollment	Cycle 1 (21-Day Cycle)			Cycle 2 (21-Day Cycle)	Cycle 3-16 (21-Day Cycle)		EOT/ET	PTFU ^b
	Cycle (C) Day (D) Visit Window	-28 to D1	Within 72 hours of first dose	C1 D1	C1 D2 & 4	C1 D3 & 5	C2 D1	Cx D1	Cx D16- 21	30 days (±2 days) after last dose	Minimum of 24 months

Cycles 1 and 3

Day 1: within 4 hours before the start of the brentuximab vedotin infusion and 30 minutes (± 25 minutes) after the end of the brentuximab vedotin infusion

Day 2: 24 hours (± 4 hours) from the start of the Day 1 dose infusion

Day 4: 72 hours (± 4 hours) from the start of the Day 1 dose infusion

Group B (consisting of half the brentuximab vedotin-treated patients):

Cycles 1 and 3

Day 1: within 4 hours before the start of the brentuximab vedotin infusion and 30 minutes (± 25 minutes) after the end of the brentuximab vedotin infusion

Day 3: 48 hours (± 4 hours) from the start of the Day 1 dose infusion

Day 5: 96 hours (± 4 hours) from the start of the Day 1 dose infusion

x **CCI**

y Immunogenicity samples in patients receiving brentuximab vedotin will be collected before dosing on Day 1 of Cycles 1, 3, 5, 7, 9, 11, 13, and 15 and at EOT.

z **CCI**

TABLE OF CONTENTS

LIST OF TABLES	16
LIST OF FIGURES.....	16
LIST OF ABBREVIATIONS AND GLOSSARY OF TERMS	17
1. BACKGROUND AND STUDY RATIONALE.....	21
1.1 Scientific Background	21
1.1.1 Disease Under Treatment: Cutaneous T-cell Lymphoma	21
1.1.2 Disease Treatment and Staging	22
1.1.3 Study Drug	24
1.2 Preclinical Experience	25
1.3 Clinical Experience	25
1.4 Study Rationale	28
1.4.1 Treatment Options in CTCL.....	28
1.4.2 Choice of Comparator.....	29
1.4.3 Summary of Study Rationale.....	30
1.5 Potential Risks and Benefits	31
2. STUDY OBJECTIVES	34
2.1 Primary Objectives	34
2.2 Secondary Objectives	35
2.3 Exploratory Objectives	35
3. STUDY ENDPOINTS.....	36
3.1 Primary Endpoint	36
3.2 Secondary Endpoints	36
3.3 Exploratory Endpoints.....	37
4. STUDY DESIGN.....	37
4.1 Overview of Study Design.....	37
4.2 Number of Patients	40
4.3 Duration of Study	40
5. STUDY POPULATION.....	41
5.1 Inclusion Criteria	41

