6. STUDY DRUG

Patients will be randomized in a 1:1 ratio to receive study treatment with either Arm 1: brentuximab vedotin, or Arm 2: bexarotene or methotrexate (for bexarotene-treated patients, study treatment will include pretherapy with fenofibrate, per Section 6.2.2). All protocol-specific criteria for administration of study drug must be met and documented prior to drug administration. Study drug will be administered only to eligible patients under the supervision of the investigator or identified subinvestigator(s).

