10.3 Monitoring of Adverse Events and Period of Observation

AEs, both nonserious and serious, will be monitored throughout the study as follows:

- AEs will be reported from the first dose of study drug through 30 days after administration of the last dose of study drug. All events relating to peripheral neuropathy regardless of seriousness will be followed for all changes in severity until resolution to baseline or study closure, whichever occurs first, and recorded in the eCRF.
- Serious pretreatment events will be reported to the Millennium Department of Pharmacovigilance or designee from the time of the signing of the informed consent form (ICF) up to first dose of study drug, but will not be recorded in the eCRF.
- Related and unrelated SAEs will be reported to the Millennium Department of Pharmacovigilance or designee from the first dose of study drug through 30 days after administration of the last dose of study drug and recorded in the eCRF. After this period only related SAEs must be reported to the Millennium Department of Pharmacovigilance or designee. SAEs should be monitored until they are resolved or are clearly determined to be due to a patient's stable or chronic condition or intercurrent illness(es).

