5.4.2 Definition of Baseline Values

Unless otherwise specified, the baseline value is defined as the value collected at the time closest to, but before, the start of study drug administration.

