5.7.2 Study Treatments

Patients will be randomized to receive study treatment, either brentuximab vedotin or bexarotene or MTX.

Brentuximab vedotin will be administered by outpatient intravenous (IV) infusion given over approximately 30 minutes on Day 1 of each 21-day cycle. The dose of brentuximab vedotin is 1.8 mg/kg. Study treatment will be administered through a dedicated IV line and cannot be mixed with other medications. Details on the dosing of study drug can be found in the protocol.

MTX will be given once weekly as a single dose of 5 to 50 mg orally. Dosages may be gradually adjusted to achieve optimal clinical response but must not exceed 50 mg/week. Once optimal clinical response is achieved, the MTX dosage should be decreased to the lowest effective dose. For patients deriving benefit, MTX dosing should be continued up to 48 weeks.

The recommended initial dose of bexarotene capsules is 300 mg/m²/day. Bexarotene capsules should be taken as a single oral daily dose with a meal. Bexarotene capsules should be continued as long as the patient is deriving benefit, up to 48 weeks. All patients (with normal or normalized triglyceride levels) who are to be given bexarotene should receive 7 days of pretherapy with fenofibrate 145 to 200 mg daily starting from Cycle 1 Day 1 (i.e., the initial dose of bexarotene starts on Day 8 of Cycle 1).

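### Unless 'study drug' is read to include fenofibrate, adverse event recording skips the first week of study treatment, in bexarotene patients only

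*Protocol*

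**What the plan says.** **The anchor.** The adverse event row of the Schedule of Events reads "Recorded from first dose of study drug through 30 days after the last dose of study drug", and protocol 10.3 repeats it: "AEs will be reported from the first dose of study drug through 30 days after administration of the last dose of study drug". SAP 5.11.1.1 (treatment-emergent events) and SAP 2.5 (Safety population) also start from a first dose of study drug. SAP 5.4.2 takes baseline as "the value collected at the time closest to, but before, the start of study drug administration".

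**Serious events before that dose.** Protocol 10.3 sends these to pharmacovigilance from consent onward, "but will not be recorded in the eCRF".

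**The fenofibrate week.** Schedule footnote t states: "Patients taking bexarotene will receive fenofibrate for a total of 7 days before the start of bexarotene dosing". Protocol section 6 adds: "for bexarotene-treated patients, study treatment will include pretherapy with fenofibrate, per Section 6.2.2". SAP 5.7.2 starts fenofibrate on Cycle 1 Day 1, so that "the initial dose of bexarotene starts on Day 8 of Cycle 1". The Day 8 start appears only in the SAP; the protocol's schedule has no fenofibrate row and no Day 8 entry.

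**The concern.** Brentuximab vedotin and methotrexate are scheduled from Cycle 1 Day 1, so their adverse event clock starts with treatment. For bexarotene patients, a week of mandated study treatment after randomisation comes before the first capsule. If the clock waits for the capsule, part of the control regimen's toxicity falls outside the safety comparison, and only in one part of one arm.

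The protocol itself expects harm from this class of drug: section 6.2.2 names raised transaminases, raised creatine kinase and muscle pain as fibrate effects. A non-serious event that is never entered in the eCRF cannot be recovered at analysis.

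**Working it through.** **1. The plan's own figure.** Pretherapy lasts 7 days from Cycle 1 Day 1, so the first bexarotene dose falls on Day 1 + 7 = Day 8. This matches SAP 5.7.2.

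**2. What 'study drug' covers.** No passage defines it for bexarotene patients.

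- *Narrow reading (fenofibrate excluded).* The Protocol Summary describes study drug as up to 16 cycles of brentuximab vedotin or 48 weeks of bexarotene or methotrexate. Protocol 6.5 contrasts study drug with other treatments active against CTCL. Protocol 7.7 counts study drug in brentuximab cycles or weeks of reference therapy. SAP 5.7.2.1 builds exposure from brentuximab vedotin, methotrexate and bexarotene doses only.
- *Broad reading (fenofibrate included).* The sentence making fenofibrate part of study treatment stands in the section titled Study Drug. Protocol 10.1.1 defines a pretreatment event by the absence of any study *medication*, and the documents switch between 'drug' and 'medication'; SAP 5.11.1.1 uses both in one sentence.

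**3. Cycle 1 Days 1 to 7 for a bexarotene patient.**

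| Item | Narrow reading | Broad reading |
|---|---|---|
| Non-serious event | Not recorded | Recorded, treatment-emergent |
| Serious event | Pharmacovigilance only; not in eCRF or treatment-emergent tables | Pharmacovigilance, eCRF and tables |
| Patient who stops that week | Outside Safety population | Inside, but with no treated cycle under SAP 5.7.2.1 |
| Gap | 7 days | 0 days |

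**4. Size under the narrow reading.**

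- Share of Cycle 1: 7/21 = 33%.
- Share of a 48-week course: 7/(48 × 7) = 7/336 = 2.1%.
- Patients affected: every bexarotene patient, but their number is not given. Assuming 25% to 75% of about 62 controls, 0.25 × 62 = 15.5 and 0.75 × 62 = 46.5, so about 16 to 47 patients, and 7 × 15.5 to 7 × 46.5 = about 109 to 326 patient-days.

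These are shares of time. The documents give no event rate for the fenofibrate week, so they cannot be turned into a number of missed events.

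**5. The 72-hour window.** The Schedule places enrolment no more than 72 hours (3 days) from first dose. If fenofibrate starts on Cycle 1 Day 1 after randomisation and 'first dose' means bexarotene, the interval is at least 7 days, so at least 7 − 3 = 4 days over. If 'first dose' means fenofibrate, the window can be met.

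**6. Baseline.** Footnote h schedules chemistry at screening, before dosing on Day 1 of each cycle, and at end of treatment. Lipids are due at screening and on Day 1 of listed cycles. Nothing is scheduled between Cycle 1 Day 1 and Day 8. The extra lipid checks in protocol 6.2.2 are counted from the start of bexarotene, the first at Day 7 after it. A baseline value affected by fenofibrate would therefore need an unscheduled test in that week.

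**The case against.** **The broad reading is available.** Protocol section 6, the pretreatment definition in 10.1.1 and the 72-hour window all fit a first dose on Day 1. SAP 5.7.2.1 defines exposure and need not govern the adverse event clock. This stands. A reader might infer that harms in the fenofibrate week are simply lost, but the documents support that only conditionally. Even on the narrow reading, serious events reach pharmacovigilance from consent.

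**Baseline is hardly touched.** A reader might also infer that change from baseline in lipids and transaminases for bexarotene is generally measured from a value that fenofibrate has already altered. The documents do not support this. Protocol 6.2.2 has lipids measured, and normalised if raised, before the pretherapy week, and no lipid or liver test is scheduled within it. Creatine kinase is not in the chemistry panel at all. Only the unscheduled-test route remains.

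**The bexarotene window is not shorter overall.** The last brentuximab dose comes 15 × 21 = 315 days after the first; adding 30 gives 345 days. Bexarotene from Day 8 to Day 336 spans 328 days; adding 30 gives 358. This is fair for full-course patients, but it does not restore the missing week. The issue is which treatment time is covered, not the length of the window.

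**The direction is against the sponsor.** Undercounting control toxicity makes brentuximab vedotin look relatively worse, and no efficacy endpoint is affected. True, and it limits the importance of the point, but the safety comparison would still be uneven.

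**Conclusion.** The point holds in conditional form, as a cheap improvement. The documents leave open whether 'study drug' includes fenofibrate, and their more common usage excludes it. A site or programmer following that usage would skip the 7 days of fenofibrate pretherapy, for bexarotene patients only, in adverse event recording, the treatment-emergent tables and Safety population membership.

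The effect is a small undercount of control toxicity: 2.1% of a 48-week course per bexarotene patient, in a number of patients that the plan does not state. It rests on the narrow reading and on the SAP's Day 8 timing; under the broad reading the gap is zero. Some reconciliation is needed either way: the narrow reading conflicts with the 72-hour window, and the broad reading leaves a fenofibrate-only patient in the Safety population with no treated cycle. Whether the sequence of fenofibrate and bexarotene is right is not judged here.

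**What to change.** - In the Schedule of Events, protocol 10.3, and SAP 2.5, 5.4.2 and 5.11.1.1, anchor adverse event and serious adverse event recording, treatment-emergent status, the Safety population and baseline to the first dose of any study treatment, stating that for bexarotene patients this includes fenofibrate. Use matching wording in protocol 8.1.3 and 8.1.9.
- Keep bexarotene exposure in SAP 5.7.2.1 measured from the first capsule, and say how a patient who took only fenofibrate is shown.
- Reconcile the 72-hour enrolment window, the bexarotene row and footnote t of the Schedule, and protocol section 6 with the timing in SAP 5.7.2.

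**Cost.** Wording in both documents. Adverse event recording starts 7 days earlier for bexarotene patients, who on the SAP's timing are already on study treatment from Cycle 1 Day 1. Control treatment-emergent counts will then include fenofibrate effects; since the first-capsule date is still needed for exposure, events with onset before it can be identified.
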